#### Risks:

Open maxillectomy is a well-established, routine treatment modality and the general risks are well known. The only extra risk involves the additional exposure to ionizing radiation, although the dose of a CBCT scan is significantly lower than that of a conventional CT of the head and neck.

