A branch of IGS, also known as computer-aided surgery or surgical navigation, allows the localization of interventional tools with respect to images acquired from various modalities, such as CT and MRI. These systems employ real-time tracking, either electromagnetic or optical, and provide feedback with visualization software. Such systems have demonstrated geometric accuracy of approximately 2 mm at the start of surgery and deteriorating by less than 1 mm by the end of the procedure, which is adequate for most operations involving rigid anatomy.

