### *Image Guidance in Head and Neck Surgery*

Anatomy related to head and neck surgical procedures includes both soft tissue structures – e.g. sinus mucosa and surrounding contents of the orbits and nasopharyngeal space – and rigid structures – e.g. the mandible, cribriform plate, and skull base. Surgical procedures in this region range from tumour ablation and neck dissection to endoscopic sinus surgery. Head and neck

surgery challenges arise due to infiltrative disease within complex anatomy surrounded by sensitive critical structures. This is compounded by large normal variations of anatomy, such as the sinus cells and clivus, and a high cost of damage to normal tissue, such as blindness (breach of optic nerves), bleeding (breach of carotid arteries), and cerebrospinal fluid leak (breach of central nervous system via the cribriform plate or clivus). Critical structures pertaining to head and neck surgeries are illustrated in Figure 1.

[figure not shown]

Figure 1. Critical structures surrounding the paranasal sinuses as demonstrated in coronal CT scans of nose and paranasal sinuses.

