## **3. STUDY DESIGN**

This is a prospective study which has the character of an exploratory pilot study, establishing the implementation of CBCT in patients undergoing maxillectomy for malignant tumours. Patients with maxillary sinus malignancies are included irrespectively of histological type, first presentation of disease or recurrence, that will undergo open maxillectomy, as indicated. This applies to stages T1-T4a for non-melanomas (SCC, adenocarcinoma, adenoid-cystic carcinoma, etc) and T3-T4a for melanomas of the maxilla. All patients will undergo preoperative MRI and planning of the resection volume using the medical imaging processing software WorldMatch. There will be two phases in this study: 1. In the first phase, three patients will undergo the standard surgical procedure and control with intraoperative CBCT, without any further resection. 2. In the second phase, three patients will undergo the same procedure as in phase 1, but will receive additional excision if the CBCT reveals residual tissue that was included in the preoperative imaging planning.

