### **Comparison of preoperative and intraoperative imaging – evaluation of resection**

Matching of the preoperative MRI (that includes the preoperatively segmented resection margins) with the intraoperative CBCT images is performed using the above mentioned imaging software WorldMatch.

- For the patients included in the first phase of the study, after the acquisition of the CBCT scans, the maxillectomy is terminated and the reconstruction of the maxilla follows according to the standard procedure. Preoperative and intraoperative imaging matching will be performed postoperatively. The matching procedure is based on the bony structures surrounding the tumor area on MRI and CBCT. The tumor area shown in MRI is expected to be occupied by air in the post-operative CBCT. Figure 3 summarizes the procedure followed for phase I patients.
- For the patients of the second phase, thorough evaluation of the matched images is performed by the head and neck surgeon, before the reconstruction of the maxilla. If the excision is fully accomplished according to the preoperative plan, then the resection procedure is terminated and the reconstruction of the maxilla follows. The surgical procedure will be continued, only in case that there is suspicious residual tumour, included in the imaging resection planning. The complementary tissue resection is limited at the level where the residual tumour is detected, based on anatomical landmarks. After the supplementary resection, a second CBCT is obtained, as described in the previous section, and the same fusion procedure with the preoperative imaging is repeated. This second imaging evaluation is used to confirm the additional excision of the residual tumour. No more than two CBCT scans will be performed. The whole procedure for phase II patients is summarized in Figure 4.

[figure not shown]

Figure 3. Flowchart of work-up for patients in phase I.

[figure not shown]

Figure 4. Flowchart of work-up for patients in phase II.

Quality assessment of the preoperative and intraoperative imaging matching will be performed using two indices:

- The *Sorensen-Dice coefficient* is a statistic used for comparing the similarity of two images. Sørensen's original formula was intended to be applied to presence/absence data, and is:

$$QS = \frac{2[A \cap B]}{[A] + [B]}$$

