A and B represent, in this case, two distinct images that are superimposed on one another (Figure 5). The index ranges between 0 and 1, depending on how complete is the overlap between the two images (0: no overlap; 1: complete overlap).

[figure not shown]

Figure 5. Two different images A and B, partially overlapping with each other.

- The *Hausdorff distance* is a metric between two point sets. It measures the extent to which each point of a set lies near some point of another set. Since an image can be considered as a set of points, Hausdorff distance can be used to determine the degree of resemblance of two images. The following formula is used to calculate the index, considering two different sets of points, A (including points  $a_1, a_2, a_3$  etc) and B (including points  $b_1, b_2, b_3$  etc):

$$H(A, B) = \max(h(A, B), h(B, A))$$

where

$$h(A, B) = \max_{a \in A} d(a, B) \text{ and } d(a, B) = \min_{b \in B} \rho(a, b)$$

$d(a, B)$  is the distance from a point  $a$  to the set  $B$ , and  $\rho(a, b)$  is a point distance in the metric space  $M$ .

Quality assessment of imaging matching will be performed after completion of the surgery.

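### The protocol calls radiation the only extra risk, yet in phase 2 the MRI-CBCT match can prompt further excision before its quality is measured, and phase 2 does not wait for the phase 1 matches

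*Protocol*

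**What the plan says.** **Risk.** Section 11.4 states: "The only extra risk involves the additional exposure to ionizing radiation". The Summary repeats this. The burden listed in both places is about 15 minutes of operating time per scan.

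**What phase 2 adds.** Under section 3, the three phase 2 patients "will receive additional excision if the CBCT reveals residual tissue that was included in the preoperative imaging planning". Section 8.3 words the trigger more narrowly: "The surgical procedure will be continued, only in case that there is suspicious residual tumour, included in the imaging resection planning". A second CBCT follows any such excision.

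**What is checked before cutting.** In phase 2, "thorough evaluation of the matched images is performed by the head and neck surgeon, before the reconstruction of the maxilla". Section 8.3 also limits the extra excision to the level where residual tumour is seen, guided by anatomical landmarks, and bases the matching on bone around the tumour.

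**When match quality is measured.** Section 8.1.1 makes match quality (Dice coefficient and Hausdorff distance) a main study parameter. Section 8.3 closes with: "Quality assessment of imaging matching will be performed after completion of the surgery". It makes no exception for phase 2.

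**Phase 1.** For these three patients, "Preoperative and intraoperative imaging matching will be performed postoperatively", and section 4.4 rules out acting on the result.

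**Local anatomy.** The introduction describes "a high cost of damage to normal tissue, such as blindness (breach of optic nerves), bleeding (breach of carotid arteries), and cerebrospinal fluid leak".

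**The concern.** The study tests whether the MRI-CBCT match is good enough to verify a resection, so its quality is not yet established. In phase 2 the same match can lead to more tissue being removed. The excision stays inside the plan only if the plan is displayed in the right place. A match error moves the display, so that tissue beyond the true plan can look like residual on one side while true residual is hidden on the other.

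The ethics committee is told that the only added risk is radiation. Excision that would not have happened outside the study is a surgical risk the study creates, even when every match is perfect.

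The error would also reach the results. A false residual that is excised would be recorded as found and cleared, and a second match with the same error would agree. That affects the complete-resection endpoint (section 8.1.1) and the residual-to-plan ratio (section 10.1), which are meant to prepare a randomised trial.

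**Working it through.** **Step 1: is radiation the only extra risk?** Under section 8.3 the surgeon operates without image guidance, on best judgement, and the CBCT comes after the resection is complete. Any excision after that point in phase 2 is prompted by the study. The burden text counts scans only: two scans give 2 × 15 = 30 minutes, with nothing for the excision between them. The statement fails for 3 of 6 patients.

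**Step 2: what stands between the match and the excision?**

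| Safeguard | In the protocol? |
|---|---|
| Surgeon evaluates the matched images before reconstruction | Yes (8.3) |
| Suspicious tumour that is also inside the plan | Yes (8.3); section 3 says tissue |
| Excision limited by anatomical landmarks | Yes (8.3) |
| Stated limit for an acceptable match | No |
| Recorded match error before excision | No; indices follow surgery (8.3) |
| Phase 2 conditional on the phase 1 matches | No |

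The checks that exist are qualitative. Phase 1 yields three matches on which nobody acts, so match quality could be seen safely before patient 4, but no rule requires anyone to look.

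**Step 3: an illustration of scale.** The documents give no MRI-CBCT match error. Assume that the plan is a sphere of radius R, that the cavity equals the plan exactly, and that the match error is a pure shift d. The overlap of two equal spheres gives the apparent residual as a fraction of the plan:

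f = 3d/(4R) − d³/(16R³)

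For d = 2 and 3 mm, the only guide is the introduction's figure for surgical navigation: "geometric accuracy of approximately 2 mm at the start of surgery and deteriorating by less than 1 mm by the end of the procedure".

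| Diameter | Volume | d = 2 mm | d = 3 mm |
|---|---|---|---|
| 30 mm | 14.1 ml | 10.0% (1.4 ml) | 14.9% (2.1 ml) |
| 40 mm | 33.5 ml | 7.5% (2.5 ml) | 11.2% (3.8 ml) |
| 60 mm | 113.1 ml | 5.0% (5.7 ml) | 7.5% (8.5 ml) |

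Example at 40 mm and 2 mm: 3×2/(4×20) − 2³/(16×20³) = 0.0750 − 0.0001 = 7.5%. At 40 mm, shifts of 1 to 5 mm give 3.7% to 18.7%. All of this apparent residual lies outside the true plan, as a crescent at most d thick. A resection that exceeds the plan by at least d shows none.

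**Step 4: would a phase 1 review suffice alone?** With 0 poor matches in 3, the exact one-sided 95% upper bound on the poor-match rate is 1 − 0.05^(1/3) = 63%. The review can catch a gross problem but cannot vouch for the next patient, so a check in each phase 2 operation is needed as well.

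**The case against.** The strongest reply is that the safeguards are real. The surgeon looks at the matched images before cutting, excision requires suspicious tumour inside the plan, landmarks limit it, and matching already rests on bone. This stands. A reader might infer that nobody examines the match until surgery is over; section 8.3 does not support that. Only the two indices wait.

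Second, standard surgery already aims at the same intended volume, so excising a true residual within the plan is in keeping with the operation. This narrows the hazard. The further excision and its time still come from the study, as does any removal beyond the true plan.

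Third, the phases are already staged, section 9.1 obliges the sponsor to suspend the study if safety is in jeopardy, and the entry under interim analysis (section 10.2) does not rule out a clinical review. All true. A reader might take that entry as forbidding such a review, but it belongs to the statistics section and says nothing of the kind. What remains is that no review is required.

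Fourth, the sphere figures are an upper case. They need an exact resection, a pure shift and a surgeon who cuts the crescent, and the shift comes from navigation, a different technology. This stands too. A reader might infer that 5% to 15% of the planned volume would be wrongly removed, or that a 2-3 mm crescent means injury to the optic nerve or carotid artery. The documents support neither.

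**Conclusion.** The point holds as a matter of text. The risk statement in the Summary and section 11.4 is wrong for phase 2. The check on the match before excision is real but has no stated limit and no record, the quantitative assessment comes after surgery, and phase 2 is not tied to the phase 1 matches. These are rules of surgical conduct and risk disclosure, so they belong in the protocol rather than in a statistical analysis plan.

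Three of six patients are exposed. The chance and size of harm cannot be estimated from the documents; the sphere table rests entirely on its assumptions. A reader might go on to infer a 3 mm acceptance limit from the navigation figure, or a rule to excise only where residual is thicker than the match error. The first has no adequate source here. The second is a clinical trade-off that could leave thin true residual to inspection alone, where the introduction reports local failure of 30% to 50%. Nor can it be said that patients are misinformed, since the consent form is not shown.

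**What to change.** 1. **Summary and section 11.4 (Risks):** add one sentence saying that in phase 2 a CBCT-prompted excision carries surgical risk and added operating time, including possible removal of tissue beyond the plan if the images are mismatched.
2. **Sections 3 and 8.3:** open phase 2 only after a documented review of match quality in the three phase 1 patients, against an acceptance limit that the team writes beforehand.
3. **Section 8.3:** in phase 2, before any CBCT-prompted excision, the surgeon checks and records the match at bony landmarks outside the resection, and rematches if it is unacceptable. Dice and Hausdorff are still computed after surgery.

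The cost is a few minutes in up to three operations and a short pause between patients 3 and 4, with no extra scan. If the phase 1 matches miss the limit, phase 2 starts later.

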#### Benefits:

For the patient: The surgeon's experience is a significant factor for complete tumor excision and, thus, for a successful maxillectomy. In this study, control of the resected area will be performed based on the comparison of the intraoperative CBCT with the preoperative imaging (MRI) planning. This way, complete tumour resection (according to imaging) will be confirmed. Resection free margins according to intraoperative imaging can potentially increase the possibility of pathologically free margins, which in turn is a major predictive factor of prolonged survival. Moreover, the use of imaging provides an additional tool for the control of the proximity to significant anatomical structures, and thus decreasing the complication rates.

Benefits in general: The use of CBCT suggests an innovative imaging technology that may have an important contribution in the radical excision of maxillary malignant tumours, affecting positively on the patients' prognosis. Thus, the current study may have a significant impact on the way the procedure is nowadays performed.

### **11.5 Compensation for injury**

The sponsor has a liability insurance which is in accordance with article 7 of the WMO.

The sponsor (also) has an insurance which is in accordance with the legal requirements in the Netherlands (Article 7 WMO). This insurance provides cover for damage to research subjects through injury or death caused by the study.

The insurance applies to the damage that becomes apparent during the study or within 4 years after the end of the study.

### **11.6 Incentives**

Not applicable

## **12. ADMINISTRATIVE ASPECTS, MONITORING AND PUBLICATION**

### **12.1 Handling and storage of data and documents**

All personal data will be handled confidentially. Data will be inputted into an Excel data form. The data form will be stored in the personal computer of the coordinating researcher. Access to the data will be allowed only to the researchers.

The handling of personal data will comply with the Dutch Personal Data Protection Act (in Dutch: De Wet Bescherming Persoonsgegevens, Wbp)

### **12.2 Amendments**

Amendments are changes made to the research after a favourable opinion by the accredited METC has been given. All amendments will be notified to the METC that gave a favourable opinion.

### **12.3 Annual progress report**

The investigator will submit a summary of the progress of the trial to the accredited METC once a year. Information will be provided on the date of inclusion of the first subject, numbers of subjects included and numbers of subjects that have completed the trial, serious adverse events/ serious adverse reactions, other problems, and amendments.

### **12.4 Temporary halt and (prematurely) end of study report**

The sponsor will notify the accredited METC of the end of the study within a period of 8 weeks. The end of the study is defined as the last patient's last visit.

The sponsor will notify the METC immediately of a temporary halt of the study, including the reason of such an action.

In case the study is ended prematurely, the sponsor will notify the accredited METC within 15 days, including the reasons for the premature termination.

Within one year after the end of the study, the sponsor will submit a final study report with the results of the study, including any publications/abstracts of the study, to the accredited METC.

## 12.5 Public disclosure and publication policy

All information resulting from this trial is considered to be confidential, at least until appropriate analysis and study coordinators of the trial have completed checking.

Any publication, abstract or presentation comprising results from the trial must be submitted for examination and approval to study coordinators.

## 13.STRUCTURED RISK ANALYSIS

Not applicable

